1.15 Baseline data

The following baseline data will be collected:

- Age

FLUid intervention and **Renal Outcome Trial** in patients undergoing major surgery: an observational single-centred study (**FLURO TRIAL**). Version 2, 31st Mar 2014

- Gender
- Admission type (elective vs. emergency)
- Type of surgery (hepatobiliary, colorectal, upper GI, orthopaedic etc.)
- If admitted to ICU: Chronic APACHE co-morbidities (including long-term dialysis)
- If admitted to ICU: APACHE-III admission diagnosis⁴²
- If admitted to ICU: Illness severity based on the on the APACHE-III risk of death score⁴²
- Baseline creatinine.
- Baseline biochemistry

(Note: - all of these data are routinely collected for quality assurance purposes or as measured as part of usual clinical care)

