1.17.2 Secondary outcome measures

- Serum electrolytes
- Acid base disturbances
- Post-operative complications
- Requirements for ICU
- Requirement for dialysis or hemofiltration
- Duration of ICU stay
- Hospital length of stay

FLUid intervention and **Renal Outcome Trial** in patients undergoing major surgery: an observational single-centred study (**FLURO TRIAL**). Version 2, 31st Mar 2014

ETHICS

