1.21 Data collection methods

The demographic, biochemical, and outcome data used in this study are already collected by the Austin Hospital for administrative and quality assurance purposes⁷.

Any ICU data are similarly collected and already provided to the Australian and New Zealand Intensive Care Society Centre for Outcome and Resource Evaluation as part of a government-funded bi-national quality assurance programme.

The only data used in this study, which are not routinely collected for quality assurance purposes, are the daily volume of study fluid administered as fluid boluses and the data relating to renal outcomes. These data will be collected by the Principle and Associate investigators.

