1.24 Adverse Events and Other Safety Aspects

Safety will be assessed throughout the study. As part of normal hospital care for all patients undergoing surgery at Austin Hospital, a complete baseline profile of each subject will be established by the treating surgical unit through medical history, clinical laboratory values, vital signs, physical assessments, and ECGs. During the course of the study, surgical and anaesthesia care, including vital signs, complete and targeted physical assessments, laboratory tests, and ECGs will be performed at in accordance with normal hospital protocols. **There will be no deviation from standard care at any time point.**

All medical and surgical changes from baseline will be monitored throughout the study by the treating units and appropriate interventions will be taken accordingly.

STATISTICAL CONSIDERATIONS

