1.26 Analysis plan

A complete description of the statistical analyses will be specified in a statistical analyses plan, finalised prior to completion of the study.

All analyses will be conducted on an intention-to-treat basis.

The primary analyses will be unadjusted analyses in which binary outcomes will be compared using relative risks with 95% confidence intervals and chi square tests and continuous outcomes will be compared with the use of mean differences and unpaired T-tests assuming that normality assumptions are met. If normality assumptions are not met then we plan to attempt simple data transformation, such as a logarithm transformation, and if this fails to proceed to a Mann-Whitney rank based test. Adjusted analyses will be performed using Poisson regression for binary

FLUid intervention and **Renal Outcome Trial** in patients undergoing major surgery: an observational single-centred study (**FLURO TRIAL**). Version 2, 31st Mar 2014

outcomes and linear regression for continuous outcomes. Baseline covariates will include age, gender, elective vs. emergency surgery, surgical specialty of admission, type of operation, and baseline serum creatinine level. Survival times will be compared using log-rank tests and presented as Kaplan-Meier curves. Multivariable models will be developed to study the predictors of AKI and the independent association between fluid choice and renal outcomes.

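### Comorbidity and illness severity are collected only for patients admitted to ICU, so the adjusted and predictor models cannot account for them in the whole cohort

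*Protocol*

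**What the plan says.** Section 1.15 lists the baseline data. Age, gender, admission type, type of surgery, baseline creatinine and baseline biochemistry are listed without condition. Three items are conditional on ICU admission: the APACHE-III admission diagnosis, chronic comorbidity ("If admitted to ICU: Chronic APACHE co-morbidities (including long-term dialysis") and severity ("If admitted to ICU: Illness severity based on the on the APACHE-III risk of death score"). Section 1.21 explains the condition, since these items come from an ICU quality-assurance programme: "Any ICU data are similarly collected and already provided to the Australian and New Zealand Intensive Care Society Centre".

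The cohort is not an ICU cohort. Section 1.13 admits any adult having surgery longer than two hours with at least one postoperative night in hospital. Section 1.14 excludes only patients under 18 and liver transplantation, so long-term dialysis patients are eligible. Section 1.17.2 lists "Requirements for ICU" as a secondary outcome.

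Section 1.26 names the adjustment set: "Baseline covariates will include age, gender, elective vs. emergency surgery, surgical specialty of admission, type of operation, and baseline serum creatinine level". It then promises multivariable models for predictors of AKI and for the independent association of fluid choice with renal outcomes. The synopsis says the same. Section 1.16 leaves fluid choice entirely to the treating clinicians.

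**The concern.** When clinicians choose the fluid, sicker patients may be given one fluid more often than another. Comorbidity is an obvious candidate both for influencing that choice and for raising the risk of AKI. An association described as independent should be adjusted for it, and a model of AKI predictors should be able to test it. Here the variable exists only for patients who reached ICU.

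This leaves the analyst two options. One is to fit the whole cohort without comorbidity, which is what section 1.26 describes. The other is to use the APACHE items and keep only ICU patients, who are selected on a study outcome that may follow the exposure.

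Dialysis status is a specific case. AKI is defined by a change in creatinine, and need for dialysis or hemofiltration is a secondary outcome. Yet outside ICU no listed item identifies a patient already on long-term dialysis. A baseline creatinine value does not establish that by itself.

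**Working it through.** The protocol gives no ICU share and no comorbidity prevalence, so it has no figure of its own to reproduce on this point. The check has three parts.

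**1. Who has which variable (protocol sections 1.15 and 1.26)**

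| Variable | Collected for | In the adjusted model |
|---|---|---|
| Age, gender, urgency | all | yes |
| Specialty, operation type | all | yes |
| Baseline creatinine | all | yes |
| Baseline biochemistry | all | not named |
| Chronic comorbidity, including long-term dialysis | ICU only | no |
| APACHE-III diagnosis and risk of death | ICU only | no |

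No listed item would let a comorbidity term be fitted in the whole cohort.

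**2. How many patients lack the data**

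Number without data = N × (1 − f), with N = 400 to 600 (section 1.9) and f the ICU share, which is assumed.

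| f (assumed) | N = 400 | N = 600 |
|---|---|---|
| 10% | 360 | 540 |
| 20% | 320 | 480 |
| 30% | 280 | 420 |
| 40% | 240 | 360 |
| 50% | 200 | 300 |
| 60% | 160 | 240 |

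The gap covers more than half of the cohort only if f is below 50%.

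**3. How much one omitted comorbidity could matter**

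The benchmark is the effect in the power statement (section 1.25): 0.14 / 0.084 = 1.67.

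For an unmeasured binary confounder with risk ratio R for AKI and prevalence p1 and p0 in the two fluid groups, the RR produced with no fluid effect is

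[1 + p1(R − 1)] / [1 + p0(R − 1)].

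R, p1 and p0 are all assumptions.

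- R = 2, 40% vs 20%: (1 + 0.40) / (1 + 0.20) = 1.40/1.20 = 1.17
- R = 3, 40% vs 20%: (1 + 0.80) / (1 + 0.40) = 1.80/1.40 = 1.29
- Milder case, R = 1.5, 30% vs 20%: 1.15/1.10 = 1.05
- Stronger case, R = 3, 50% vs 20%: 2.00/1.40 = 1.43

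If the imbalance runs the other way, the two central cases become 1/1.17 = 0.86 and 1/1.29 = 0.78, and would mask an effect instead of creating one.

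The formula treats the comorbidity as wholly unadjusted. Correlation with age, urgency, operation type or creatinine, all of which are in the model, would generally make the remaining bias smaller.

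**The case against.** The strongest reply is that the plan already adjusts for a good deal. Age, urgency, specialty, operation type and baseline creatinine are substantial confounders for a creatinine-based outcome, and creatinine captures part of chronic kidney disease. This stands. A reader might infer that the main confounders are missing or that residual confounding cannot be reduced. The documents do not support either, because six covariates are collected and adjusted for in everyone. What is missing is comorbidity and severity.

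A reader might also infer that most of the cohort lacks these data. That may be so, but no ICU share is stated. The exact statement is every patient not admitted to ICU.

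Thirdly, the primary analysis is explicitly unadjusted, so this gap does not alter it. The study is also presented as preliminary evidence for a later interventional trial. Both points stand and limit the consequence to the adjusted and predictor models.

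Fourthly, no section says the APACHE items will enter a model, so selection on ICU admission is a risk only if someone uses them that way. Section 1.15 also does not say that ICU admission must be postoperative, so for some patients it may not follow the fluid. Both points are correct.

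Lastly, covariate choice can be left to the statistical analysis plan. That is fair for the list in section 1.26. It does not answer section 1.15, because an analysis plan cannot adjust for a variable that was never collected. The protocol's general statement that data come from medical records does not make comorbidity a study variable. Section 1.21 points the other way: beyond routine quality-assurance data it adds only fluid volumes and renal outcomes.

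**Conclusion.** The point holds for data collection and for the adjusted and predictor models. Comorbidity, including long-term dialysis status, and illness severity are study data only for patients admitted to ICU. An association adjusted as section 1.26 describes is therefore independent of the six named covariates, not of comorbidity.

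The size is uncertain. With a confounder RR of 2 to 3 and prevalence of 40% versus 20%, the spurious RR is about 1.17 to 1.29 before any correlation with the adjusted covariates. Milder and stronger assumptions give 1.05 to 1.43. None of these inputs comes from the protocol. Against a planning RR of 1.67, the central range is large enough to affect interpretation, but too small to account for an effect of that size alone.

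This is a worthwhile, inexpensive improvement and not a flaw that invalidates the study.

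**What to change.** - **Section 1.15:** for every patient, collect a short comorbidity set from the preoperative medical history or anaesthetic record, for example long-term dialysis, chronic kidney disease, diabetes, heart failure, hypertension, and ASA class if charted. Record not documented separately from absent.
- **Section 1.21:** add these items and their source to the data collected by the investigators. As written, the section leaves no room for them.
- **Section 1.26 and the synopsis:** add the set to the covariates of the adjusted and predictor models.
- **APACHE-III items:** state that they are descriptive, for ICU patients only.

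The source should exist. Section 1.24 says that under normal care "a complete baseline profile of each subject will be established by the treating surgical unit through medical history". The change also stays within the protocol's rule of using only data already gathered for clinical or quality-assurance purposes.

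The cost is modest abstraction time per patient and a few more model terms. The terms are not free. At the planning rates the cohort would yield between about 400 × 0.084 = 34 and 600 × 0.14 = 84 AKI events, and specialty and operation type already use several terms. The set should therefore be short and fixed in advance.

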1.16 Study treatments

This is not an interventional study. This is an observational study only. Therefore, there is no departure from standard care at any stage. It only involves the collection of data that has already been collected for clinical or quality assurance purposes. Perioperative care and fluid intervention will remain completely at the discretion of the treating clinicians.

[figure not shown]
1.17 Treatment allocation

Non-applicable. There is no departure from standard care at any stage. It only involves the collection of data that has already been collected for clinical or quality assurance purposes.

Total study duration: 12 weeks

TREATMENT SCHEME

All adult patients (≥ 18 years) undergoing major surgery (> 2 hours) and requiring at least one overnight post-operative hospital stay:

Outcome measures

1.17.1 General

The primary outcome measure will be acute kidney injury (RIFLE-criteria) defines as AKI, defined as an increase in creatinine greater than 25% or 0.5 mg/dL (44 $\mu\text{mol/L}$) from baseline to peak value within the first 48-hours postoperatively.

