1.3 Coordinating Department

Department of Anaesthesia
Austin Hospital
Heidelberg, Victoria
Australia

STUDY SYNOPSIS

Title:	Fluid intervention and Renal Outcome Trial in patients undergoing major surgery: an observational single-centred study (FLURO Trial).
Short Title:	Fluid therapy in major surgery.
Design:	Single-centred, prospective observational study. Information about intravenous fluid intervention (type of fluid and amount) for adult patients undergoing major surgery (duration >2 hours and at least one overnight stay) will be collected over a 6-week period. The effects of these fluids on renal function will be investigated.
Study Centers:	1
Hospital:	Austin Hospital
Study question:	What are the association between perioperative intravenous fluids and renal function in adult patients undergoing major surgery at a University teaching hospital.
Study Objectives:	To determine the association between perioperative intravenous fluids and renal function in adult patients undergoing major surgery.
Primary Outcome:	Acute kidney injury (AKI), defined by an increase in creatinine greater than 25% or 0.5 mg/dL (44 µmol/L) from baseline to peak value within the first 72-hours postoperatively.
Secondary Outcomes:	Serum electrolytes Acid base disturbances Post-operative complications Requirements for ICU Requirement for dialysis or hemofiltration Duration of ICU stay Hospital length of stay In-hospital mortality
Inclusion criteria:	Adult patients ≥ 18 years Elective or emergency surgery Surgery duration > 2 hours Requiring at least one overnight stay
Exclusion criterion:	<18 years in age Liver transplantation
Number of planned Subjects:	400-600

FLUId intervention and **Renal Outcome Trial** in patients undergoing major surgery: an observational single-centred study (**FLURO TRIAL**). Version 2, 31st Mar 2014

Investigational product:	Nil
Safety considerations:	
This is an observational study only. There is no departure from standard care at any stage. It only involves the collection of data that has already been collected for clinical or quality assurance purposes.
 
Perioperative care and fluid intervention will remain completely at the discretion of the treating clinicians.

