1.6 Study design

This study aims to observe the association between perioperative intravenous fluids have and renal function in adult patients undergoing major surgery. **It is a single-centered, prospective observational study and therefore does not change the standard of care in any way.** All patients undergoing surgery at Austin Hospital will be given the perioperative fluids at discretion of the treating clinicians.

The study will be conducted over a 12-week period, allowing a wide variety of amount and type of fluids given to the patients. Austin Hospital staff specialists in anaesthesia agree that on the basis of current evidence, Saline (0.9%), Plasmalyte or Hartmann's solution are equally acceptable for crystalloid fluid therapy in every situation requiring major surgery with the exclusion of surgery for liver transplantation where specific hospital perioperative fluid protocols are used in these settings.

As there is no departure from standard care for this study, Saline (0.9%), Plasmalyte and Hartmann's solution will be available for administration to all patients undergoing major surgery. In the situations, where, in the opinion of the treating anaesthetist or clinician, there is a clinical indication for other types of fluid e.g. colloids, blood, dextrose etc, again there will be no deviation from standard care in any way.

All adult patients who undergo major surgery will be analysed. The primary outcome will be the proportion of patients with kidney injury or failure based on established criteria⁵. Secondary outcomes will include delta creatinine (the difference between baseline and peak creatinine), serum electrolyte levels, acid base disturbances, requirements for ICU, duration of ICU stay, hospital length of stay, complications and in-hospital mortality.

All of the data required for this study are collected routinely as part of standard clinical care and/or quality assurance activities⁶.

FLUid intervention and **Renal Outcome Trial** in patients undergoing major surgery: an observational single-centred study (**FLURO TRIAL**). Version 2, 31st Mar 2014

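### The primary AKI rule rests on creatinine alone, so a patient who starts dialysis before a qualifying rise is recorded can be scored AKI-free

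*Protocol*

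**What the plan says.** The operational definition of the primary outcome appears twice in the protocol, and both times it is a creatinine rise and nothing else.

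- Section 1.17.1: AKI is "defined as an increase in creatinine greater than 25% or 0.5 mg/dL (44 $\mu\text{mol/L}$) from baseline to peak value", "within the first 48-hours postoperatively".
- Study Synopsis, Primary Outcome: "Acute kidney injury (AKI), defined by an increase in creatinine greater than 25% or 0.5 mg/dL", here measured "from baseline to peak value within the first 72-hours postoperatively".

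Section 1.17.1 also attaches the RIFLE label, and section 1.6 says "The primary outcome will be the proportion of patients with kidney injury or failure based on established criteria". Neither place writes out a dialysis component.

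Renal replacement is handled apart from AKI. "Requirement for dialysis or hemofiltration" is a secondary outcome in section 1.17.2 and in the synopsis, and it is a separate item in the Objectives. Section 1.6 adds a continuous measure: "Secondary outcomes will include delta creatinine (the difference between baseline and peak creatinine". No section says that starting dialysis counts as AKI, or how creatinine measured after dialysis starts enters the peak or the delta.

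Two further points bear on any repair. Section 1.14 excludes only patients under 18 and liver transplantation, so patients already on dialysis can be enrolled. Section 1.15 lists long-term dialysis as a baseline item only for patients admitted to ICU.

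**The concern.** Dialysis and haemofiltration lower serum creatinine. Once treatment begins, the observed peak may be lower than the value the patient would otherwise have reached. If treatment starts before the threshold is crossed, or before a sample that would show the crossing, the written rule returns no AKI for a patient who has just been given renal replacement. If the threshold had already been crossed, AKI is scored correctly, but the delta can stop at the last value before treatment.

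The protocol's own rationale makes this relevant to the comparison. Its Background cites a chloride-restrictive strategy associated with less AKI and less renal replacement therapy, and a surgical cohort in which Plasmalyte was associated with less renal failure requiring dialysis. An AKI definition that can leave out newly dialysed patients sits badly with that rationale. The protocol also says the study is to supply preliminary outcome data for the power calculations of later trials, so the definition may carry forward.

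**Working it through.** The protocol gives no figure for this point. Its only design figure is the power statement in section 1.25, and nothing here depends on it. The check is to apply the written rule to creatinine courses.

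**Rule.** With baseline b and observed peak p in µmol/L, and reading the two limbs as alternatives, AKI is scored if p − b > 0.25·b or p − b > 44. The limbs coincide at b = 44 / 0.25 = 176. Below that baseline the 25% limb is the easier to meet; above it, the 44 µmol/L limb is.

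**Courses.** All values are assumed. In each, the observed peak is the value when dialysis starts, because later values are lower.

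| Baseline | Value at start | Rise | Rise, % | Scored |
|---|---|---|---|---|
| 80 | 98 | 18 | 22.5 | no AKI |
| 200 | 240 | 40 | 20.0 | no AKI |
| 176 | 219 | 43 | 24.4 | no AKI |
| 80 | 160 | 80 | 100 | AKI |

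The first three patients are newly dialysed and enter the primary analysis as AKI-free. The fourth is classified correctly, so a miss requires treatment (or a gap in sampling) to come before the rise passes both 25% and 44 µmol/L.

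**Delta creatinine.** The first patient has a delta of 18. An undialysed patient with the same baseline must exceed 0.25 × 80 = 20 merely to count as AKI, so every such AKI case has a larger delta than this dialysed patient. The fourth patient's delta is 80 whatever level would have been reached without treatment.

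**Number of patients.** The protocol gives no dialysis rate, so this is a range under stated assumptions. Let r be the share starting dialysis in the window (assumed 0.5% to 2%) and m the share of those missed by the creatinine rule (assumed 10% to 100%). Missed patients = N × r × m.

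- N = 400: 400 × 0.005 × 0.10 = 0.2, up to 400 × 0.02 × 1 = 8.
- N = 600: 600 × 0.005 × 0.10 = 0.3, up to 600 × 0.02 × 1 = 12.

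The upper ends need every newly dialysed patient to be missed, which a low threshold applied to the peak makes unlikely.

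**The case against.** The best case for the current text has four parts.

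1. **Narrow reach.** A single value more than 25% above baseline before dialysis is enough to score AKI, so most patients whose creatinine rises before treatment are captured. This stands, and it limits the size of the problem.

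2. **Dialysis is reported anyway.** It is a named outcome, so an excess under one fluid would appear there. This is true, and a reader who infers that the protocol conceals dialysis-related harm goes too far. It does not cure the primary outcome, which can still list a newly dialysed patient as free of kidney injury.

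3. **Not every early dialysis is kidney injury.** A patient haemofiltered for acidosis or an electrolyte disturbance before creatinine rises may not have renal failure, and the Background itself allows that hyperchloraemic acidosis may be benign. This stands as a cost of the repair.

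4. **Handling creatinine after dialysis starts is a matter for the SAP.** For delta creatinine this has some force. It does not for the primary endpoint, whose definition the protocol fixes itself.

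A reader might also infer that the rule pulls the relative risk towards no difference. The documents do not support a figure or even a direction. Take the 14% and 8.4% of section 1.25 with an assumed 250 per group: 0.14 × 250 = 35 and 0.084 × 250 = 21 events, relative risk 35/21 = 1.67. Four misses, all under saline, give 31/21 = 1.48. Four misses, all in the comparator, give 35/17 = 2.06. Proportional misses give (35 − 5)/(21 − 3) = 1.67, unchanged. The number and placement of misses are free choices. The rates describe RIFLE injury and failure in critically ill patients, not this 25% rule after surgery.

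Nor is delta creatinine truncated in every newly dialysed patient: where the true peak came before treatment, nothing is lost.

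**Conclusion.** The point holds in a limited form. As written, the primary AKI rule can classify a newly dialysed patient as AKI-free, and delta creatinine can be cut off at the pre-dialysis value. Both follow directly from the text, given only that dialysis lowers creatinine. The number affected is probably small, and the documents do not allow it, or any effect on the relative risk, to be estimated. The case for changing the definition is that the patients at risk of misclassification have received renal replacement, and that the repair is cheap. It is a worthwhile improvement, not a flaw that invalidates the primary analysis.

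The differing AKI windows matter here only because a dialysis component needs a single window to refer to.

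**What to change.** - **Definition.** In the synopsis and section 1.17.1, define AKI as the stated creatinine rise, or new dialysis or haemofiltration started within the same postoperative window in a patient not on dialysis before surgery. Reconcile the 48-hour and 72-hour statements first. Keep dialysis as a separate secondary outcome as well.
- **Data.** Record preoperative dialysis status for all patients, not only those admitted to ICU, and the time at which dialysis or haemofiltration started. Both should come from the medical record; section 1.21 already has the investigators collecting the renal outcome data.
- **Delta creatinine.** Report the number of newly dialysed patients by fluid. Add a sensitivity analysis, for example a separate rank-based comparison in which these patients are ranked worst. It has to be specified in its own right: section 1.26 plans mean differences with t-tests and linear regression, and uses Mann-Whitney only if normality and transformation both fail. A worst rank has no place in a mean difference.

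**Cost.** One clause in the outcome definition, two extra data items and one sensitivity analysis. Clinical care is unaffected; only the scoring changes. The downside is that dialysis started for a non-renal reason would count as an event. Such cases can be listed with the reason for starting.
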